### Participant newsletter:

In addition to the letter (described above) that participants will receive after they have completed their treatment, we will send a series of newsletters to each participant between 3-11 months after randomisation. We anticipate sending one newsletter every 4-6 weeks, but this exact schedule will be determined through consultation with our PPIE group. These newsletters will be sent via email/letter (depending on participant preference) and will remind participants that they are still in the study, explain the importance of completing the outcomes and give some update on study progress, e.g. numbers of participants who have been recruited. The exact format and content of each newsletter will be developed through ongoing consultation with our PPIE group.

### Incentives to complete outcome data

As explained above, all participants, (irrespective of group allocation), will receive £20 when they receive the invitation to complete 6-month outcomes and £20 when they receive the intervention to complete the 12-month outcomes. These payments will be made by bank transfer as this is the only mechanism available to University of Salford staff to reimburse participants.

## 8.9 Qualitative assessments and evaluation

There will be two components to the embedded qualitative study, both of which will inform our programme theory. The first will focus on understanding the impact of the CMT intervention on daily living, self-management and patient's beliefs around knee OA. Secondly, working with the physiotherapists, we will explore potential barriers and facilitators to delivery and implementation of the CMT intervention within an NHS setting informed by the Normalisation Process Theory (NPT) [34]. NPT will provide a framework to understand how CMT can become routine with current NHS practice by exploring physiotherapist engagement, barriers to implementation, benefits, and sense-making around CMT.

The qualitative work with patient participants will build on our earlier work investigating patient and physiotherapy perceptions immediately after CMT [35]. In this study, we will interview participants 6-10 months after they have completed the intervention to explore longer-term implementation of CMT concepts occurring after exposure to the intervention. To facilitate this work, and minimise the burden on participants, we will use a baseline qualitative survey (see 'Baseline qualitative survey') to capture understanding and perceptions of knee OA pain and views of prognosis before the intervention. This survey will be completed at the same time as the baseline outcomes by all participants. We will then interview a sample of participants in the CMT arm after the 12-month outcome data collection point. These interviews will take place 13-14 months after randomisation, and this will remove the potential for bias in trial outcomes which could result from contact with a qualitative researcher in one arm of the study

We will purposively recruit a minimum of 15 patients who have received the CMT intervention for interview. To be included in the qualitative work, we will invite patients who have a varying attendance recorded (see Section 6.5). Specifically, we will invite participants who have attended four or less sessions (low attendance), those who have attended five or six sessions (medium attendance) and those who have attended all seven sessions

(maximum attendance). By including participants with varying attendance, we will explore what elements of the intervention have been implemented in self-management behaviours and attitudes towards knee OA. These data will be triangulated with outcome scores and baseline beliefs. While we will aim to interview a minimum of 15 participants, the exact number interviewed will be determined by information power through ongoing analysis during the interview period.

Each participant selected for the qualitative work will be invited to attend an online interview. We will provide guidance to help set up the call for those who find it difficult to engage with technology and offer a telephone interview for those unable to use the internet. Through semi-structured interviews, guided by a topic guide (see 'Topic guide (patient interview)') and the baseline qualitative survey, we will gain insight into the participants' personal experiences/opinions of the CMT intervention (usability, adherence, effectiveness, and acceptability) and its influence on their perceptions of knee OA. These questions were co-developed with our advisory panel. The data from the baseline survey will be analysed separately to the interviews. Both the qualitative survey and the interviews will be analysed with template thematic analysis [36] allowing for us to develop coding whilst considering *a priori* themes developed from self-management literature. Template thematic analysis will be appropriate to use for the larger dataset from the survey.

The second part of our qualitative work will be carried out with the physiotherapists who deliver the CMT intervention during this study. Participation in this qualitative work will be optional. For those who consent, we will run a series of online focus groups, including at least three physiotherapists who have delivered their final CMT intervention session within 3 months of the date of the focus group. A qualitative researcher will lead the focus group and, using the topic guide (see 'Topic guide (physiotherapist focus group)'), will explore implementation of CMT, gaining insight into the training course and also exploring barriers and facilitators to implementation of CMT on the NHS. This topic guide has been developed to address core constructs of the NPT. These data will be analysed through framework analysis [37] so we can use a deductive approach and map the data on the constructs of NPT [34]. We can then use an inductive approach to allow for us to capture all the insight into how we can inform an implementation strategy for CMT for the NHS (if the results of the trial support future rollout).

## 8.10 Withdrawal criteria

Participants will be able to withdraw from the BEPKO-3 trial at any time without affecting the clinical care they receive. However, if participants are in the CMT arm, they will no longer receive the CMT treatment. This is clearly explained in the participant consent form.

If participants do decide to withdraw, they will be provided with two options:

1. Discontinue the intervention: Withdraw from receiving the CMT treatment (if in the CMT arm) but still provide follow-up outcome data at 6 months and 12 months.
2. Complete withdrawal from the trial. If they choose this option, they will not be contacted at the follow-up timepoints. However, their baseline data will be retained.

Any change in participation and/or withdrawal from the study will be clearly documented in the study records.

## 8.11 End of trial

The end of the study is defined as the return of the final (12-month) questionnaire data from the final participant in the trial or the final interview. The research team at the University of Salford will notify the Sponsor administration team, participating sites, and REC within 90 days of the end of study. The final report required by the REC and HRA will be submitted within 12 months of the end of study.

## 9 ADVERSE EVENT MANAGEMENT

### 9.1 Definitions

#### 9.1.1 Adverse Events (AE)

An Adverse Event (AE) is defined as any untoward medical occurrence involving a participant, which does not necessarily have a causal relationship with the intervention or study.

##### AEs exempt from formal recording

For the intervention group, common AEs listed below that are identified during or after intervention sessions will be recorded on the treatment log (not an AE form), for clinical purposes only:

- Any accidents (e.g. falls) which occur during normal daily activities
- Exacerbation of pre-existing musculoskeletal conditions (including knee pain) which last no more than five days

Any AEs that are not listed above should be recorded using the AE form (See 'Adverse events form'). Forms should be completed by the treating physiotherapist as soon as possible after becoming aware of the AE and sent to the study team. All AEs should be assessed within 24 hours of identification to check if they constitute a 'Serious Adverse Event' as per section 9.1.2 below. If assessed as a Serious Adverse Event, it should be reported within 24 hours, following the procedures outlined in section 9.2.4.

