### 3.3 Secondary Outcome measures and endpoints

- Composite WOMAC score [19] at 6-months post-randomisation
- WOMAC pain subscale [19] at 6- and 12-months post-randomisation
- WOMAC function subscale [19] at 6- and 12-months post-randomisation
- WOMAC stiffness subscale [19] at 6- and 12-months post-randomisation
- Global assessment of knee symptoms (GAKS) at 6- and 12-months post-randomisation [24]

- Pain catastrophizing scale (PCS) [25] at 6- and 12-months post-randomisation
- Pain self-efficacy questionnaire (PSEQ) [26] at 6- and 12-months post-randomisation
- Impact of knee OA on capacity to work will be measured with the Work Productivity and Activity Impairment Questionnaire (WPAI-OA) [27] at 6- and 12-months post-randomisation.
- Health-related quality of life will be measured using the EQ-5D-5L at 6- and 12-months post-randomisation. The EQ-5D-5L [28] is a validated measure of health-related quality of life in terms of 5 dimensions (mobility, ability to self-care, ability to undertake usual activities, pain and discomfort, anxiety and depression) each with 5 levels of severity.
- Healthcare resource use at 6- and 12-months will be measured via a custom questionnaire, based on the Client Services Receipt Inventory. Included within this questionnaire will be additional physiotherapy (above that provided to the CMT arm), GP appointments, corticosteroid injections, surgery, imaging, hospital stays and medication use.
- All-cause mortality.
- Adverse events attributable to the trial.
- Serious adverse events.

Our choice of outcomes includes instruments to capture pain, stiffness, activity limitation, psychological factors, global assessment of knee symptoms, quality of life, healthcare resource utilisation and adverse events, including mortality. This outcome set is sufficiently broad to include all components of a core outcome set recommended by OMERACT-OARSI (Outcome Measures in Rheumatology-Osteoarthritis Research Society International) for clinical trials in knee osteoarthritis [24].

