#### Component 4 (Contextual triggers):

In the fourth component participants learn that anticipating pain-provoking tasks can become associated with increased flexor tone and inappropriate contraction of the quadriceps muscles. They also learn that common daily activities, such as working at a computer, may trigger elevated flexor tone. To address these 'conditioned' responses participants are guided to mentally rehearse specific situations without triggering undesired increases in abdominal tone (monitored through visual inspection of abdominal wall excursion) or quadriceps activity (monitored via EMG). In the final stages of this component participants learn to initiate potentially pain provoking activities, such as stair ascent/descent without inappropriate activation of the quadriceps muscles.

Component 5 (Functional integration):

The final component focuses on integrating the learning from the previous four components. The goal is to enable participants to perform a full range of functional activities with minimal pain. Participants select activities from a comprehensive set that covers the full range of tasks assessed by the WOMAC questionnaire score [19]. This includes standing, walking, stair ascent/descent, bending, dressing etc. Guided by the physiotherapist, the participants practice performing each task with an optimal pattern of postural tone and without inappropriate activation of the quadriceps muscles.

Intervention delivery, home practice & self-management:

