### 9.2.2 Recording and assessing AEs/SAEs

Participants in the intervention group will be asked about any potential AEs at the start of each face-to-face physiotherapy session. In addition, during the session the treating physiotherapist will monitor for any indications of an AE. Potentially AEs will be evaluated by the treating physiotherapist with follow-up contact from the research team to confirm the details. Participants in the intervention group will also be provided with contact details (generic email address and phone number) for the study team. Whilst participants will not be actively encouraged to report AEs via this route, they may seek advice and help from the study team which may result in AEs being disclosed/discussed. Any AEs, with the exception of those listed in Section 9.1.1, will be recorded on the AE form and stored on the secure trial database unless they fulfil the criteria for a 'Serious Adverse Event' in which case they will be reported to the sponsor via the SAE form (see Section 9.2.3 below).

All AEs should be assessed by an appropriately qualified member of the study team within 72 hours of identification to determine if they meet the criteria to be reported as SAEs as defined in Section 9.1.2. If any AEs meet these criteria, they must be reported to the sponsor within a further 24 hours. If the follow-up questionnaire received from a participant indicates events that may fulfil an SAE, then they should be contacted for further information and an SAE form completed if applicable.

All SAEs should be reported to study team (using the document 'Serious Adverse Event Form'), irrespective of their relationship to the intervention unless they are exempt from reporting (see Section 9.1.2). Once received, the study team review the SAE and request further information if required from the treating physiotherapist or participant appropriate.

The causality of SAEs (i.e. relationship to study intervention) will be assessed by the chief investigator and another appropriately delegated member of the trial team using the classifications in Table 5 below.

Table 3: SAE Causal relationships

Relationship to study intervention	Description
Unrelated	There is no evidence of any causal relationship.

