## 11 DATA HANDLING

### 11.1 Data collection processes

A secure and auditable trial database will be created using the REDCap platform and used to store all clinical data for the study. This database will be built and hosted by Northern Care Alliance (NCA) and will be a web-based application. The database will enable customisable user rights to restrict data entry, export or viewing and will incorporate full audit trails to log user activity and data input. The system will be configured to comply with NHS Digital Data Security & Protection Toolkit (DSPT) requirements, ICH-GCP recommendations and 21 CFR Part 11 (US FDA electronic records standard). To meet these requirements, the system will incorporate full audit trails, role-based access, and two-factor authentication.

Entry into the database will be either from participants themselves or via transfer of data collected by study staff from paper questionnaires or following telephone call by study staff. Details of adverse events will be entered by the trial manager. Data on KL-grade (radiographic severity) will also be entered into the trial database by the trial manager.

Clinical records and treatment logs for participants who receive the CMT treatment will be stored on a secure digital platform, Microsoft OneDrive, which will only be accessible by the lead physiotherapist (or physiotherapist responsible for monitoring intervention fidelity) and the treating physiotherapists. To facilitate this, we will provide each physiotherapist with a University of Salford registered laptop device.

Screening data on eligibility criteria along will be stored on a password protected file with the secure Microsoft OneDrive environment. Contact details for participants, including GP contact details, will be stored on another password protected file with the Microsoft OneDrive environment. All consent forms and data access forms will be scanned and stored electronically. Access to documents which contain personal data (e.g. name and contact details) will be managed by the CI and trial manager.

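### Section 9.1.1 keeps non-serious daily-life falls and short pain flares in the CMT arm off the AE form whether or not CMT caused them, so such events cannot count in the attributable-AE outcome

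*Protocol*

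**What the plan says.** Protocol section 9.1.1 names two event types in the CMT arm that do not need an AE form. The first is "Any accidents (e.g. falls) which occur during normal daily activities". The second is "Exacerbation of pre-existing musculoskeletal conditions (including knee pain) which last no more than five days". Both "will be recorded on the treatment log (not an AE form), for clinical purposes only". Neither carries a condition on cause.

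Section 9.2.2 repeats the carve-out: "Any AEs, with the exception of those listed in Section 9.1.1, will be recorded on the AE form and stored on the secure trial database". It specifies causality assessment for serious events: "The causality of SAEs (i.e. relationship to study intervention) will be assessed by the chief investigator", with a second delegated team member, on the Table 3 scale. No matching step is given for non-serious events.

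Section 3.3 lists "Adverse events attributable to the trial" as a secondary outcome, with serious adverse events as a separate item.

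Section 6.2 describes where CMT is used. Component 4 has participants begin tasks such as "stair ascent/descent without inappropriate activation of the quadriceps muscles". Component 5 trains ordinary tasks including standing, walking and dressing. Participants take three or four challenges home between sessions and are expected to carry the skills into everyday life.

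**The concern.** The exemption looks like a filter for background events that any group of people with knee OA would have. For most interventions, the setting of the event (daily life rather than the clinic) would be a fair stand-in for unrelated to treatment. For CMT it is a poor one, because daily life is where the treatment is meant to take effect. The filter therefore removes related and unrelated events alike, while the outcome it feeds is defined by relatedness.

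At stake is the meaning of a low count. Section 6.2 reports no adverse events in over 200 people treated so far, and section 14.1 plans wider NHS delivery if the results support it. A small number of attributable AEs would be read as evidence of safety, yet for these two event types it would partly reflect the recording rule.

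**Working it through.** No arithmetic in the protocol bears on this point, so the check traces each type of event from the recording rule to the outcome.

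**Step 1: is there any other route from the treatment log to the outcome?** Section 6.5 says which log items are moved to the trial database: the dates of the first and last sessions and the number attended. Table 1 adds clinical notes and an engagement score, and the score is kept out of the outcome analysis. Section 8.7 says that, of the log data, only attendance enters the final analysis. Section 11.1 stores the logs on a platform separate from the trial database, "which will only be accessible by the lead physiotherapist (or physiotherapist responsible for monitoring intervention fidelity) and the treating physiotherapists". No transfer of exempt events is described.

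**Step 2: could the six-month questionnaire recover them?** Section 9.2.1 says that it asks about possible SAEs. Non-serious events are not sought there.

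**Step 3: follow each event type in the CMT arm.**

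| Event | AE form and trial database | Outcome it can reach |
|---|---|---|
| Non-serious daily-life fall, not caused by CMT | No | None, and none is needed |
| Non-serious daily-life fall, caused by CMT | No | None |
| Non-serious flare of up to five days, caused by CMT | No | None |
| Flare of more than five days | Yes | Attributable AEs |
| Fall during a CMT session | Yes | Attributable AEs |
| Skin reaction or dizziness | Yes | Attributable AEs |
| Event meeting SAE criteria, including a serious fall at home | SAE form | SAEs |

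The last row holds because sections 9.1.1 and 9.2.2 require a seriousness check on all AEs, and the only SAE exemption in section 9.1.2 is for elective or pre-planned treatment.

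**Step 4: read the rows together.** The second and third rows are where sections 3.3, 9.1.1 and 9.2.2 conflict. Such an event belongs to the outcome by definition and is excluded from it by the recording rule. For these events the error has one direction, since they can only be left out.

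**Step 5: the remaining rows.** Flares over five days, in-session falls, skin reactions and dizziness reach the AE form, but section 9.2.2 does not say who decides whether they are attributable, or on what scale.

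**The case against.** The best defence is that this is a deliberate choice in a low-risk pragmatic trial. Control participants are asked only about possible SAEs, and only at six months (section 9.2.1), so counting every background fall and flare in one arm would give a figure with no comparator. WOMAC and GAKS would show lasting knee worsening in both arms. This stands as an argument against recording everything. It does not justify excluding events judged to be caused by CMT, because the listed outcome is attributable events. Nor would questionnaires at 6 and 12 months pick up a fall or a brief flare during treatment.

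A second defence is that the wording may be meant to separate background accidents from prescribed practice. Section 6.2 does not name stairs among the home challenges, and Component 5 practice is guided by the physiotherapist. That is a fair reading, but section 9.1.1 does not say it, and section 6.2 expects the skills to be used in everyday life. The ambiguity itself needs resolving.

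Third, the AE form, the TSC charter and any SAP are not shown, and one of them may say how non-serious AEs are judged attributable. That could answer Step 5. It would not help exempt events, which never reach the form.

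Three stronger inferences are tempting and are not supported:

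- **That the most plausible harms of CMT are shut out of the safety outcome.** The protocol does not rank harms. The two it singles out for monitoring in section 6.2, skin reaction and dizziness, are not exempt.
- **That nobody with oversight would know of these events.** The lead physiotherapist can open the logs and sits on the TMG. Section 6.5 has the trial manager or another unblinded team member transfer log data. Section 9.2.2 provides for research-team follow-up of potential AEs. What is closed is the route to the database and the outcome.
- **That a count of lost events can be given.** If 10% to 40% of participants fell in a year (an assumption; the documents give no rate), six months would bring 126 × 0.10 × 0.5 = 6.3 to 126 × 0.40 × 0.5 = 25.2 participants with a fall. Over about eight weeks of sessions it would be 126 × 0.10 × 8/52 = 1.9 to 126 × 0.40 × 8/52 = 7.8. These are all falls, not falls caused by CMT, so they do not measure the loss.

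**Conclusion.** The point holds in a limited form. As written, a non-serious daily-life fall, or a non-serious flare of up to five days, that is caused by CMT cannot enter the trial database or the attributable-AE outcome. This is a conflict between sections 3.3, 9.1.1 and 9.2.2. It biases that outcome downward for these two event types, by an amount that the documents do not allow one to compute. The conclusion rests on applying section 9.1.1 literally and on section 6.5 listing everything that leaves the log for the database. It needs no assumed event rate. The primary outcome and the SAE outcome are unaffected, and the events remain available for clinical care. It is worth correcting before recruitment advances, because relatedness that is not judged at the time is hard to reconstruct later.

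**What to change.** - **Section 9.1.1:** keep both exemptions, but limit them to events judged unrelated to a CMT session or to home practice of CMT. Any other event of these types goes on the AE form.
- **Section 9.2.2:** apply the Table 3 relationship scale to non-serious AEs recorded on the AE form as well as to SAEs, and say who makes the judgement. Section 9.2.4 already treats possible or stronger as related for SAE reporting; the same cut would let the section 3.3 outcome be derived consistently.
- **Reporting:** present these events as a descriptive listing for the CMT arm, with no between-arm comparison, since the control arm is not asked about non-serious events.

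The cost is a wording amendment, some extra AE forms and a short relatedness judgement for events that the physiotherapists already ask about at each session and already log. No new participant contact is needed. The judgement is partly subjective and would begin with the treating physiotherapist, so the research-team follow-up in section 9.2.2 should cover it. Recording every background fall in the CMT arm is not needed.
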